### 7.1.2. Serious Adverse Events

**Serious Adverse Event is defined as any untoward medical occurrence that, at any dose:**

**A. Results in death**

**B. Is life-threatening**

NOTE: The term 'life-threatening' in the definition of 'serious' refers to an event in which the subject was at risk of death at the time of the event. It does not refer to an event, which hypothetically might have caused death, if it were more severe.

**C. Requires hospitalization or prolongation of existing hospitalization**

NOTE: In general, hospitalization signifies that the subject has been detained (usually involving at least an overnight stay) at the hospital or emergency ward for observation and/or treatment that would not have been appropriate in the physician's office or out-patient setting. Complications that occur during hospitalization are AEs. If a complication prolongs hospitalization or fulfills any other serious criteria, the event is serious. When in doubt as to whether "hospitalization" occurred or was necessary, the AE should be considered serious.

Hospitalization for elective treatment of a pre-existing condition that did not worsen from baseline is not considered an AE.

**D. Results in disability/incapacity**

NOTE: The term disability means a substantial disruption of a person's ability to conduct normal life functions.

This definition is not intended to include experiences of relatively minor medical significance such as uncomplicated headache, nausea, vomiting, diarrhea, influenza, and accidental trauma (e.g. sprained ankle) which may interfere or prevent everyday life functions but do not constitute a substantial disruption.

**E. Is a congenital anomaly/birth defect**

**F. Other Situations**

1. Medical or scientific judgment should be exercised in deciding whether reporting is appropriate in other situations, such as important medical events that may not be immediately life-threatening or result in death or hospitalization but may jeopardize the subject or may require medical or surgical intervention to prevent one of the other outcomes listed in the above definition. These should also be

Document Name	207583 Protocol.docx		
Type	Version	Document Identifier	Effective Date
elido_clinical_doc	3.0; Most-Recent; Effective; CURRENT	090032d580d40cd1	18-May-2017 10:48:45
Reason For Issue	Auto Issue		

considered serious.

2. Examples of such events are invasive or malignant cancers, intensive treatment in an emergency room or at home for allergic bronchospasm, blood dyscrasias or convulsions that do not result in hospitalization or development of drug dependency or drug abuse or reports of spontaneous abortion.

## 7.2. Recording Adverse Events and Serious Adverse Events

### Recording of adverse events and serious adverse events:

1. The investigator or site staff will be responsible for detecting, documenting and reporting events that meet the definition of an AE or SAE.
2. The investigator or site staff will then record all relevant information regarding an AE/SAE in the CRF.
3. There may be instances when copies of medical records for certain cases are requested by GSK. In this instance, all subject identifiers, with the exception of the subject number, will be blinded on the copies of the medical records prior to submission to GSK.
4. The investigator will attempt to establish a diagnosis of the event based on signs, symptoms, and/or other clinical information. In such cases, the diagnosis will be documented as the AE/SAE and not the individual signs/symptoms. Clinical AEs will be described by diagnosis and not by symptoms when possible (e.g., upper respiratory tract infection, seasonal allergy, etc. instead of runny nose).
5. AEs will be collected from the start of the provisional MEDU irradiation procedure and until 5 days following last administration of the study product.
6. SAEs will be collected over the same time period as stated above for AEs. However, any SAEs assessed as **related** to study participation (e.g., investigational product, protocol mandated procedures, invasive tests, or change in existing therapy) or related to a GSK concomitant medication will be recorded from the time a subject consents to participate in the study up to and including any follow-up contact.
7. Medical conditions reported prior to the time period for reporting AEs/SAEs should be recorded as part of the subject's medical history.

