## SCHEDEULE OF EVENTS

Procedure/Assessment	Visit 1	Visit 2  0-7 Days after Visit 1	Visit 3 1 Day after Visit 2	Visit 4  0-7 Days after Visit 3	Visit 5 1 Day after Visit 4
	Subject Screening	Provisional MED Irradiation (UV exposure)	Provisional MED Determination	Test Irradiation (UV exposure)	MEDp and MEDu Determination and SPF Calculation for Test and Reference Sunscreens
Informed Consent	X				
Demographics	X				
Medical History	X				
Current / Concomitant Medication	X	X 	X	X 	X
Individual Typology Angle (ITA ° )	X				
Fitzpatrick Skin Type Assessment	X				
In/Exclusion Criteria	X	X 			
Subject Eligibility	X	X 			
Continued Eligibility		X 	X	X 	X
Randomisation		X			
Provisional Minimum Erythema Dose (MEDu) Irradiation		X			
Visual Grading of Exposure Sub-Sites (Test Sites) 			X		X
Study Product Application to Randomly Assigned Test Sites on the Back				X	
Study Irradiation				X	
Adverse Events		X	X	X 	X
Subject Discharge from Study					X

1. Visit 2 may be combined with Visit 1; Visit 4 may be combined with Visit 3. If these visits are not combined, they must happen within 7 calendar days of one another. Therefore, the total duration of the study for each subject could range from 3 to 16 calendar days.
2. Not required if this visit is combined with the previous visit.
3. To include a review of exclusion criteria in Appendix 2.
4. Visual Grading of skin must happen 16-24 hours after irradiation.

Document Name	207583 Protocol.docx		
Type	Version	Document Identifier	Effective Date
eldo_clinical_doc	3.0; Most-Recent; Effective; CURRENT	090032d580d40cd1	18-May-2017 10:48:45
Reason For Issue	Auto Issue		

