### 4.4. Withdrawal/ Stopping Criteria

A subject may withdraw from the study at any time at his/her own request, or may be withdrawn at any time at the discretion of the investigator for safety, behavioural or administrative reasons.

If the reason for removal of a subject from the study is an Adverse Event (AE) or an abnormal laboratory test result, the principal specific event or test will be recorded on the case report form (CRF). If a subject is withdrawn from the study because of a product limiting AE, thorough efforts should be clearly made to document the

 GlaxoSmithKline	Document Name	207583 Protocol.docx		
	Type	Version	Document Identifier	Effective Date
	elido_clinical_doc	3.0; Most-Recent; Effective; CURRENT	090032d580d40cd1	18-May-2017 10:48:45
	Reason For Issue	Auto Issue		

outcome. Any AEs ongoing at the final visit will be followed up until resolved, the condition stabilizes, is otherwise explained, or the subject is lost to follow-up.

The following actions must be taken in relation to a subject who fails to attend the clinic for a required study visit:

1. The site must attempt to contact the subject and re-schedule the missed visit as soon as possible.
2. The site must counsel the subject on the importance of maintaining the assigned visit schedule and ascertain whether or not the subject wishes to and/or should continue in the study.
3. In cases where the subject is deemed 'lost to follow up', the investigator or designee must make every effort to regain contact with the subject (where possible, at least 2 telephone calls). The contact attempt should be documented in the subject's record.

Should the subject continue to be unreachable, only then will he/she be considered to have withdrawn from the study with a primary reason of "Lost to Follow-up".

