#### 7.4. Reporting Adverse Events and Serious Adverse Events

##### AE Reporting to GSKCH:

1. AEs will be recorded in the AE section of the CRF.
2. Medical conditions recorded by the subject on a diary card or similar document that meet the definition of an AE must also be recorded in the AE section of the CRF, if not previously well-characterized by the investigator in the subject's medical history.
3. AEs elicited by the investigator in a standard manner at the study visits should also be recorded in the AE section of the CRF. The investigator or designee must ask the subject the following question during each visit including any

Document Name	207583 Protocol.docx		
Type	Version	Document Identifier	Effective Date
eldo_clinical_doc	3.0; Most-Recent; Effective; CURRENT	090032d580d40cd1	18-May-2017 10:48:45
Reason For Issue	Auto Issue		

follow-up visits: ***“Have you felt unwell, experienced any symptoms or taken any medication (since your last visit) (today) (since your last dose) (since the last session)?”***

4. The medically qualified investigator should review adverse events in a timely manner; this review should be documented in writing in the source document or in the CRF.
5. After the study is completed at a given site, and the site has received their study data on Compact Discs (CDs), the electronic data collection tool will be removed from the internet to prevent the entry of new data or changes to existing data.

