## 7.5. Follow-up of Adverse Events and Serious Adverse Events

### **Follow-up of AEs and SAEs:**

1. After the initial report, the investigator is required to proactively follow up with each subject and provide further information on the subject's condition.
2. All AEs/SAEs will be followed until resolution, until the condition stabilizes, until the event is otherwise explained, or until the subject is lost to follow-up.
3. The investigator is obligated to perform or arrange for the conduct of supplemental measurements and/or evaluations as may be indicated or as requested by GSK to elucidate as fully as possible the nature and/or causality of the AE or SAE.
4. Investigators are not obliged to actively seek AEs or SAEs in former subjects. However, if the investigator learns of any SAE, including the death, at any time after a subject has been discharged from the study, and considers the event reasonably related to the investigational product or study participation, the investigator will promptly notify GSKCH.
5. The investigator will submit any updated SAE data to GSK within the designated reporting time frames.

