1.4 Timepoints and visit windows

Deviations from the scheduled assessment times must be avoided. The following are the required assessment time windows for the determination of the SPF:

Visit	Time window
Visit 2	0-7 days after Visit 1 (allowed to be combined with Visit 1)
Visit 3	1 day after Visit 2
Visit 4	0-7 days after Visit 3 (allowed to be combined with Visit 3)
Visit 5	1 day after Visit 4

Visual grading of skin at Visit 3 must happen 16-24 hours after irradiation at Visit 2. Visual grading of skin at Visit 5 must happen 16-24 hours after irradiation at Visit 4.

No visit windows are applicable for in vitro determination of the UVAPF of the test products since this part of the study does not involve human subjects.

2 Data analysis

Data analysis will be performed by inVentiv Health Clinical. Prior to database hard lock a Blind Data Review Meeting (BDRM) will be conducted in which various aspects of the trial will be discussed and agreed. The statistical analysis software used will be SAS® version 9.4.

Except as described below, all listings will be produced for all randomized subjects.

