2.5.4 Safety

2.5.4.1 Adverse events and Serious Adverse Events

All adverse events (AEs) will be summarized by primary system organ class and preferred term.

Treatment emergent adverse events (TEAEs), defined as the AEs reported after study product application, will be summarized by the number and percentage of subjects having any adverse event, any adverse event in each System Organ Class, and the number of occurrences of each individual adverse event ([Table 14.3.1.1](#)). All TEAEs will also be tabulated by severity ([Table 14.3.1.2](#)). Treatment emergent AEs suspected of a relationship to study medication will be presented in a similar manner ([Table 14.3.1.3](#)). For treatment related AEs, these will also be presented by severity ([Table 14.3.1.4](#)).

Deaths occurring during treatment (if any) will be listed ([Listing 14.3.2.1](#)) by treatment, including the date and study day of death, and the principal cause of death. Non-fatal serious adverse events causing study treatment discontinuation will be listed ([Listing 14.3.2.2](#)).

AEs will be collected from the start of provisional MEDu irradiation procedure until 5 days after the last administration of the study product. SAEs however, if assessed as related to study participation or related to a GSK concomitant medication will be recorded from the time a subject consents to participate in the study up to and including any follow-up contact.

All AEs will be listed in [Listing 16.2.7.1](#) for randomized subjects and [Listing 16.2.7.2](#) for [non-randomized subjects](#).

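### The SAP classes adverse events as treatment emergent by time of report instead of onset; secondarily, the 5-day collection window runs about 4 days past the last planned enquiry

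*Protocol*

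**What the plan says.** **Classification.** SAP 2.5.4.1 makes an AE treatment emergent (a TEAE) if it is reported once product has been applied. It sets no condition on when the event began. Tables 14.3.1.1 to 14.3.1.4 are built on this class, and Table 14.3.1.1 is a top-line output in SAP 4.4. Protocol 9.3.3 plans only a listing by subject, so the SAP is the sole source of the definition.

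**Recording period.** Protocol 7.2: "AEs will be collected from the start of the provisional MEDU irradiation procedure and until 5 days following last administration of the study product". SAP 2.5.4.1 agrees: "AEs will be collected from the start of provisional MEDu irradiation procedure until 5 days after the last administration of the study product". Product is applied only at Visit 4.

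**Schedule.** SAP 1.4 places Visit 5 "1 day after Visit 4", and the Protocol Schedule of Events puts "Subject Discharge from Study" at Visit 5. AE checks are marked at Visits 2, 3, 4 and 5. In the Visit 4 lists (Protocol Synopsis, Protocol 3.1, SAP 1.1.1) the AE item comes last, after application and UV exposure.

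**Enquiry and follow-up.** Protocol 7.4 ties the AE question to visits: "The investigator or designee must ask the subject the following question during each visit including any"; the sentence goes on to name follow-up visits, but none is scheduled. Protocol 4.4 covers known events: "Any AEs ongoing at the final visit will be followed up until resolved, the condition stabilizes". Protocol 7.5 adds: "Investigators are not obliged to actively seek AEs or SAEs in former subjects".

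**The concern.** A treatment-emergent class is meant to separate events that could follow the product in time from those that could not. Recording begins at Visit 2, so the database will hold a period in which no product has been applied. A rule based on report time does not separate that period cleanly: what counts is when the subject was asked, not when the event started. Protocol 7.1.1 (events meeting the AE definition, item 3) adds a second route, because it also counts a condition first detected after product administration even if it was there before the study. Under the SAP wording that is a TEAE too.

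The window raises a different problem. AE frequency and severity is a stated secondary endpoint. If the report cites a 5-day post-application period while planned enquiry covers about 1 day, an absence of later reactions may be read as observed when nobody was due to ask.

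**Working it through.** **1. TEAE rule.** Inputs (Schedule of Events, SAP 1.4): Visit 3 is 1 day after Visit 2, and Visit 4 is 0 to 7 days after Visit 3.

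- Recorded period before application = 1 + (0 to 7) = 1 to 8 days.
- Part of it after the Visit 3 AE check = 0 to 7 days.

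The two rules compared by case:

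| Case | Report rule | Onset rule |
|---|---|---|
| Onset between Visits 2 and 3, reported at Visit 3 | Not a TEAE | Not a TEAE |
| Onset between Visit 3 and a separate Visit 4, first reported after application | TEAE | Not a TEAE |
| Condition present before the study, first detected after application | TEAE | Not a TEAE |
| Onset after application | TEAE | TEAE |

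The second row is the main exposure. Where Visits 3 and 4 are separate and the listed order is followed, the scheduled AE question comes after application. An event cannot be reported before it starts, so every onset-based TEAE is also a report-based one. The SAP rule can therefore add events to the tables but cannot remove any.

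Effect of one subject on a row with no other event, taking the planned 5 to 8 randomised subjects as the denominator: 1/8 = 12.5%; 1/5 = 20%.

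**2. Window against schedule.** The plan's own duration first: "the total duration of the study for each subject could range from 3 to 16 calendar days". With Visit 1 as day 1 throughout:

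- Shortest: Visits 1 and 2 on day 1, Visits 3 and 4 on day 2, Visit 5 on day 3. Window closes on day 2 + 5 = 7.
- Longest: Visit 2 on day 8, Visit 3 on day 9, Visit 4 on day 16, Visit 5 on day 17. Window closes on day 16 + 5 = 21.

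The plan's 3 counts Visit 1 as day 1, while its 16 is days elapsed since Visit 1. On one convention the range is 3 to 17 (inclusive) or 2 to 16 (elapsed). The gap does not depend on this: 7 − 3 = 4 and 21 − 17 = 4 days, or 4/5 = 80% of the stated window.

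In hours, grading at Visit 5 is 16 to 24 h after irradiation ends. Ignoring the time from application to the end of irradiation, 120 − 24 = 96 h to 120 − 16 = 104 h lie after it (80% to 87%). Protocol 6.4.4 adds a wait of 15 to 30 minutes before exposure: 120 − 24.5 = 95.5 h (79.6%) to 120 − 16.25 = 103.75 h (86.5%). Irradiation time would lower these somewhat, but its duration is not stated.

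**The case against.** **On the TEAE rule.** The wording may be loose for events that occur after application: Listing 16.2.7.1 already gives study day relative to first treatment. The AE check at Visit 3 catches most earlier events. Before a separate Visit 4 application, concomitant medication and continued eligibility are reviewed, which may bring an event to light. The rule over-includes and so conceals nothing. With so few subjects, a reader can see each onset in the listing. Causality is assessed separately under Protocol 7.3.

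Most of this stands and narrows the exposure. It would be too strong to infer that every AE starting between Visit 2 and application is misclassified; the main case is onset between Visit 3 and a separate Visit 4. But the SAP offers no onset rule to fall back on, a programmer will follow the text, and the listing does not correct the tables.

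**On the window.** A reader might infer that the documents contradict themselves, that events after Visit 5 cannot be recorded, or that a 5-day contact was required and left out. The documents support none of these. Collected can mean recordable. Protocol 7.4 mentions follow-up visits, and 7.2 mentions follow-up contact for related serious events. Data entry closes only after the study is completed at the site (7.4). Protocol 7.5 does not define former subjects, so it does not clearly override the 5-day window. Consent material, which is not available here, may tell subjects to report late reactions. What remains is narrower: no enquiry about new events is planned after Visit 5, and neither document says so.

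**Conclusion.** The TEAE definition is wrong as written and should be changed. It can place events that preceded any product in the treatment-emergent tables. The exposure is up to 7 days per subject between Visit 3 and Visit 4, plus pre-existing conditions detected late. One such subject moves an otherwise empty row by 12.5 to 20 percentage points. That figure is simply 1/n and assumes all 5 to 8 planned subjects are in the safety population.

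The window is a secondary point of reconciliation: about 4 of the 5 stated days have no planned enquiry, whatever the visit spacing. Later events can still be recorded if volunteered or at an unscheduled contact, so this is a gap in planned ascertainment and does not bar collection.

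The documents give no AE rate, so no number of missed or misclassified events can be given. The effect stays within the secondary safety endpoint; SPF and UVAPF are untouched.

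**What to change.** **SAP 2.5.4.1, definition.** Define a TEAE as an AE with onset on or after the first product application, using the start date and start time already planned for Listing 16.2.7.1. Count an AE that starts on the application day with no start time as treatment emergent. The readable text does not say whether application time is a CRF field (part of Protocol 6.4.3 is redacted); if it is not available, treat same-day events in the same way. Events before application stay in the listing.

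**Protocol 7.2, SAP 2.5.4.1 and the safety report, window.** Reconcile these with the Schedule of Events by stating that active enquiry ends at Visit 5 and that later events within the 5 days come from spontaneous reports only. A scheduled contact at day 5 would be an added procedure and is not needed to make the documents agree.

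Cost: one reworded definition, one missing-time rule, and one sentence in each of three places. No new AE data, visits or subjects are needed.

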## 7.3. Evaluating Adverse Events and Serious Adverse Events

### Assessment of Intensity:

The investigator or designee will make an assessment of intensity for each AE and SAE reported during the study and will assign it to one of the following categories:

1. Mild: An event that is easily tolerated by the subject, causing minimal discomfort and not interfering with everyday activities.
2. Moderate: An event that is sufficiently discomforting to interfere with normal

Document Name	207583 Protocol.docx		
Type	Version	Document Identifier	Effective Date
elido_clinical_doc	3.0; Most-Recent; Effective; CURRENT	090032d580d40cd1	18-May-2017 10:48:45
Reason For Issue	Auto Issue		

everyday activities

3. Severe: An event that prevents normal everyday activities. An AE that is assessed as severe will not be confused with an SAE. Severity is a category utilized for rating the intensity of an event; and both AEs and SAEs can be assessed as severe.

Note: An event is defined as 'serious' when it meets at least one of the pre-defined outcomes as described in the definition of an SAE.

#### Assessment of Causality:

1. The investigator is obligated to assess the relationship between study product and the occurrence of each AE/SAE.
2. A "reasonable possibility" is meant to convey that there are facts/evidence or arguments to suggest a causal relationship, rather than a relationship cannot be ruled out.
3. The investigator will use clinical judgment to determine the relationship.
4. Alternative causes, such as natural history of the underlying diseases, concomitant therapy, other risk factors, and the temporal relationship of the event to the study product will be considered and investigated.
5. The investigator will also consult the Safety Statement, in the determination of his/her assessment.
6. For each AE/SAE the investigator **must** document in the medical notes (source document) or CRF that he/she has reviewed the AE/SAE and has provided an assessment of causality.
7. There may be situations when an SAE has occurred and the investigator has minimal information to include in the initial report to GSK. **However, it is very important that the investigator always make an assessment of causality for every event prior to the initial transmission of the SAE data to GSK.**
8. The investigator may change his/her opinion of causality in light of follow-up information, amending the SAE data collection tool accordingly.
9. The causality assessment is one of the criteria used when determining regulatory reporting requirements.

